2.1 Changes to Study Protocol 3. Study Objectives	
4. Study Design	.3
5. Sample Size Calculation	.4
6. Reporting of Patients Baseline Characteristics	.4
7. Study Endpoints	.4
 7.1 Number of dose titrations performed up to days 12-14 7.2 Secondary Endpoints	.4 .5 .5 .5 .5 .6 .6
7. References	. /

1. Executive Summary

Title	A Randomized Controlled Trial to Assess the Clinical Benefits of a			
	Pharmacogenetics-Guided Dosing Regimen for Calculating			
	Warfarin Maintenance Dose			
Sponsor	National Medical Research Council			
Principal Investigator	[name].			
Study Agent	Warfarin (Marevan®)			
Study Design	This is a multicentre, open-label, randomised (1:1) controlled trial			
	which uses a non-inferiority study design.			
	Primary analysis will be based on intention-to-treat.			
Sample Size	The sample size of 270 provides 80% power to detect a non-			
	inferiority margin of 0.5 with a one-sided alpha of 0.05, given a			
	between-group difference in mean number of dose titrations of 1.0			
	and common standard deviation of 1.4.			
	Assuming an attrition rate of 15%, 320 patients would be enrolled			
	and randomly allocated 1:1 to a study group.			
Interim Analysis	None			
Patients	Eligible patients must be at least 18 years of age; have a new			
	indication for warfarin; have no previous history of liver disease,			
	malabsorption syndrome or chronic diarrheal conditions; do not			
	have uncontrolled hypertension, peptic ulcer disease or any			
	medical condition deemed unfit for warfarin therapy.			
Drimony Objective	Written informed consent is required prior to enrolment. To compare pharmacogenetics-guided versus traditional dosing of			
Primary Objective	warfarin in terms of anticoagulation control parameters			
Treatment Duration	Patients will be followed for 3 months from treatment initiation			
Primary Endpoint	 Number of dose titrations performed up to days 12-14 			
Secondary Endpoints	2. Time to stable INR*			
	3. Number of dose adjustments at 1, 2 and 3 months			
	4. Number of INR assessments at 1, 2 and 3 months			
	5. Proportion of patients whose INR exceeded 3.0			
	6. Frequency of bleeding episodes			
	7. Incidence of recurrent venous thromboembolism with 90 days			
	of diagnosis			
	8. Percentage of patients achieving target INR by days 12-14*			
	9. Percentage of time spent within therapeutic INR range*			
	10. Accuracy (MPE%) and precision (RMSE%) of the			
	pharmacogenetic maintenance dose-prediction model			
	* These endpoints use target INR range >1.9 and \leq 3.1			
Study Sites	1. National University Hospital, Singapore			
	2. University of Malaya Medical Centre, Malaysia			
	3. Tan Tock Seng Hospital, Singapore			
Clinical Trial Registration				
Details	NCT00700895.			

2. Introduction

The Statistical Analysis Plan (SAP) provides a comprehensive and detailed description of the statistical design and methodologies, including pre-planned analyses for the study "A Randomized Controlled Trial to Assess the Clinical Benefits of a Pharmacogenetics-Guided Dosing Regimen for Calculating Warfarin Maintenance Dose" (Protocol No: PG01/11/06).

2.1 Changes to Study Protocol

The SAP summarises the statistical design and methodologies presented in the April 2014 version of the study protocol; and where differences exist, supersedes the study protocol. Any changes to the study protocol as listed in this SAP have been submitted to and approved by the Domain Specific Review Board (DSRB) of the National Healthcare Group (NHG). Any differences with the study protocol are clearly described, and the rationale for the amendments explained.

3. Study Objectives

The primary objective is to assess the clinical benefits of genotype-guided dosing of warfarin against the traditional mode of dosing which uses only clinical factors.

The secondary objective is to prospectively evaluate the accuracy and precision of the pharmacogenetic dose-prediction model used to calculate the maintenance dose for patients in the pharmacogenetics arm [1].

4. Study Design

This is a multicentre, open-label, randomised controlled trial which uses a noninferiority study design. Patients newly indicated for warfarin therapy will be randomised 1:1 to receive pharmacogenetics-guided or the traditional dosing regimen. The therapeutic International Normalised Ratio (INR) range is considered to be >1.9 and \leq 3.1.

The disposition of patients who were screened for eligibility will be summarised in a CONSORT flow diagram [2].

Protocol Version and Date: Version 13, April 2014 SAP Version and Date: Version 1, June 2016

5. Sample Size Calculation

The sample size of 270 (135 in each study arm) provides 80% power to detect a non-inferiority margin of 0.5 with a one-sided alpha of 0.05, given a betweengroup difference in mean number of dose titrations of 1.0 and common standard deviation of 1.4. Primary analysis will use the intention-to-treat population, which will include patients evaluable for the primary endpoint at 12–14 days

Assuming an attrition rate of 15% after randomisation, approximately 320 patients would be enrolled and randomly allocated in a 1:1 fashion to the study groups.

6. Reporting of Patients Baseline Characteristics

Baseline characteristics between the two study groups will be summarised using mean and standard deviation for continuous variables that are normally distributed, or using median and interquartile range if they are skewed. Baseline categorical variables will be described using frequency and percentages. Primary analysis will be carried out based on the principle of intention-to-treat. No interim analyses will be performed. As the study uses a non-inferiority design, a one-sided significance of 5% will be used for statistical comparisons throughout the study.

7. Study Endpoints

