7.2 Secondary Endpoints

7.2.1 Time to stable INR

The time to stable INR is defined as the number of days from randomisation to attaining therapeutic INR for two consecutive measurements that are at least 7 days apart. Patients who were lost to follow-up or did not achieve stable INR during the observation period would be censored at their last follow-up visit. The comparison between study groups will be described using the Kaplan Meier curves and the logrank test. The effect estimate will be quantified using the hazard ratio (HR) and its associated 95% CI.

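### The stated 80% power does not follow from the plan's inputs, which give 90%, and the one-sided 5% level of the primary non-inferiority test has no reason of its own

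*SAP*

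**What the plan says.** Sections 1 and 5 of the SAP give the same sample-size statement. In section 5, the size of 270 (135 per arm) "provides 80% power to detect a non-inferiority margin of 0.5 with a one-sided alpha of 0.05", given a "difference in mean number of dose titrations of 1.0" and a "common standard deviation of 1.4". About 320 patients are to be enrolled to allow for 15% attrition.

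Section 6 sets the level for the whole analysis: "As the study uses a non-inferiority design, a one-sided significance of 5% will be used for statistical comparisons throughout the study". No other reason for 5% is given.

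Section 7.1 compares the mean number of titrations with a Student's t-test. It mentions neither the margin nor a confidence interval. Section 7.2.1 reports the "hazard ratio (HR) and its associated 95% CI", and sections 7.2.4 and 7.2.5 also use 95% intervals, for risk ratios.

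**The concern.** There are two linked problems.

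**The power figure.** The stated power, margin, SD, level and sample size do not fit together under any reading of the 1.0 that was tried. A reader cannot tell whether the trial was designed for 80% or 90% power, or what true difference was assumed.

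**The level.** A non-inferiority question is naturally one-sided. That does not settle how large the error in that direction may be. One-sided 5% corresponds to a two-sided 90% CI. The SAP's secondary estimates carry 95% intervals, which correspond to one-sided 2.5%. The primary claim is therefore judged more leniently than the intervals printed beside it would suggest. If the pharmacogenetic arm truly needed 0.5 more titrations, it would pass 1 time in 20 at 5% and 1 time in 40 at 2.5%.

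This is the primary comparison, and the only endpoint for which the SAP gives a margin. Because section 7.1 names only a t-test, the decision rule has to be inferred from section 5.

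**Working it through.** **Inputs from SAP section 5:** margin 0.5; SD 1.4; 135 evaluable per arm; one-sided alpha 0.05; stated power 80%; difference 1.0, direction not given; attrition 15%.

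**Assumption of this check:** the distance *d* between the true difference and the margin is 0.5. This follows from a true difference of zero, or from |1.0 − 0.5| = 0.5. Other distances are shown in step 3.

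**1. The plan's own figure.** Normal approximation: n per arm = 2·SD²·(z₁₋α + z_power)² / d², where 2 × 1.4² / 0.5² = 15.68.

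- One-sided 5%, 80% power: 15.68 × (1.645 + 0.842)² ≈ 97 per arm, 194 in total.
- One-sided 5%, 90% power: 15.68 × (1.645 + 1.282)² ≈ 134.3, so 135 per arm, 270 in total.

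The planned 270 is the 90% figure. The attrition step agrees with the plan: 270 / 0.85 = 318, against about 320.

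**2. Power of 135 per arm, noncentral t.** SE = 1.4 × √(2/135) = 0.1704; noncentrality = 0.5 / 0.1704 = 2.934; df = 268.

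| One-sided alpha | Power with 135 per arm | n per arm for 80% | n per arm for 90% | Largest observed disadvantage that passes |
|---|---|---|---|---|
| 5% | 90.0% | 98 | 135 | 0.5 − 1.651 × 0.1704 = 0.219 |
| 2.5% | 83.2% | 125 | 166 | 0.5 − 1.969 × 0.1704 = 0.165 |

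The normal approximation gives 90.1% and 83.5%, with 97 and 124 per arm for 80%.

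**3. Does another reading of the 1.0 rescue the 80%?**

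- 1.0 fewer titrations in the pharmacogenetic arm: *d* = 1.5, power essentially 100% at either level.
- *d* = 1.0 (the 1.0 used alone, or a true benefit of 0.5): power above 99.99% at either level.
- 1.0 more titrations in the pharmacogenetic arm: beyond the margin, so non-inferiority would be false.

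None gives 80%. With *d* = 0.5 and one-sided 5%, 135 per arm would give 80% only if the SD were about 1.65.

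**4. Sensitivity at 2.5%.** Power stays at 80% up to an SD of about 1.46.

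**5. Cost if 90% was the real target.** At one-sided 2.5%, 166 per arm is 332 evaluable, and 332 / 0.85 = 391 enrolled, against about 320 planned.

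**The case against.** The strongest reply is that one-sided 5% was pre-specified, is disclosed, and agrees across sections 1, 5 and 6, with no interim looks. Nothing in the SAP sets 2.5% as its standard. That stands: the level is a lenient choice given no reason, and not an internal contradiction.

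A reader might infer that the stated 80% power calls for one-sided 2.5%, so that the trial accepts twice the false-claim risk it needs. The documents do not support this. Power does not fix alpha. On the same inputs, 135 per arm gives 80% power at a one-sided alpha of about 1.8%, so the argument does not single out 2.5%. Nor is zero true difference the plan's stated input; the SAP states 1.0.

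It is also fair to object that the stricter level is not free. Because 270 fits a 90% design exactly, the 80% may be the misprint, and moving to 2.5% would then miss the intended power. This stands and is counted as a cost below.

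Two smaller points are also right. Section 6 applies one-sided 5% to the secondary tests too, so changing the primary rule does not remove the mismatch there. And halving alpha does nothing about bias from open-label dosing decisions.

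**Conclusion.** The sample-size statement is wrong as written. With a distance of 0.5 to the margin, an SD of 1.4 and 135 per arm, power at one-sided 5% is 90.0% and not 80%. The role of the 1.0 must be stated before any power figure can be checked properly.

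The 5% level is coherent but unexplained. At one-sided 2.5% the planned size still gives 83.2%, above the only power figure the SAP states. The practical difference is modest: an observed disadvantage between about 0.165 and 0.219 titrations would be declared non-inferior while its 95% CI crosses 0.5.

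These figures assume a zero true difference (or the |1.0 − 0.5| reading), a common SD of 1.4 and 135 evaluable patients in each arm. It would go too far to conclude that the SAP contradicts itself on alpha, or that the stricter level costs nothing.

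**What to change.** In SAP sections 1 and 5, state the direction of the 1.0 and whether it is an assumed true difference or something else, and correct the power figure.

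In sections 5, 6 and 7.1, write the decision rule: non-inferiority is declared if the upper limit of the two-sided 95% CI for the difference in mean titrations (pharmacogenetic minus traditional) is below 0.5. State that 135 evaluable per arm gives 83% power at one-sided 2.5% for zero true difference and an SD of 1.4. In section 6, say which level applies to the secondary comparisons, so that their tests agree with their 95% intervals.

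The cost is SAP wording and no more patients, with power falling from 90% to 83% at zero true difference. There is almost no loss if the pharmacogenetic arm truly needs 0.5 or more fewer titrations. If the sponsor's target was 90%, it has to accept 83% or enrol about 391.

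If the sponsor prefers to keep one-sided 5%, the SAP should give a reason, restate the power as 90%, and report the primary result with a 90% CI against the margin and the 95% CI alongside.

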7.1 Number of dose titrations performed up to days 12-14

The primary endpoint is the number of dose titrations performed up to 12-14 days following the initiation of warfarin therapy. The average number of dose titration will be compared between study groups using the Student's t-test.

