4.3 Patient data collection

Baseline characteristics will be obtained from all patients accrued into the study. These include race, age, sex, weight, height, liver and renal function, and concomitant medications. The INR values and dates of tests for each patient will also be recorded, together with any tests of the prothrombin time (PT), partial thromboplastin time (PTT). Each adjustment in warfarin dose will also be recorded and the corresponding INR checked within 1 week. Patients potentially eligible for this study will be screened from both the inpatient and outpatient services. INR will be performed using the standard venous blood sample.

[figure not shown]

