4.4 Derivation of Warfarin Dosing Model with Validation

A total of 220 complete datasets were available for constructing the warfarin dose requirement linear regression model. Demographic predictors used for model-building included age, weight, sex, ethnic group (Chinese, Malay, Indian, Others), serum albumin concentration, INR and the presence of CYP2C9*3 variant and VKOR-381 CC genotypes. Log-transformation was applied to warfarin doses to achieve normality in its distribution. Univariate anaylses were conducted to retain the closely associated predictors for further model building. Only those variables with p < 0.1 in the initial analysis were considered as sufficiently associated with warfarin dose and retained for further model-building. Only those predictors showing statistical significance of p < 0.05 and did not demonstrate collinearity were retained in the final model. A data-splitting method that randomly assigned approximately 50% of the available dataset for model building and the remaining half for model validation was employed.

One hundred and eleven patients were randomly selected into the model-building dataset and the remaining 109 formed the validation cohort. The initial multiple linear regression model using the logarithmic derivation of warfarin dose featured the patient age, body weight, Indian and Chinese ethnic groups as well as the pharmacogenetic predictors *VKORC1-381* CC, *VKORC1-381* TC, *CYP2C9*2* and *CYP2C9*3* as predictors. It exhibited an r^2 of 0.609. Collinearity checks of the model showed tolerance values of between 0.287 for *VKORC1-381* CC genotype to 0.898 for age, and corresponding VIF values of 3.49 to 1.114. However, the p values of the 2 ethnic group and *CYP2C9*2* predictors did not reach statistical significance (p>0.05). Hence, they were removed from the final regression model. Details of the final linear model are available on request. Standardized residuals were between -2.9 to 2.0. Overall, this model showed only a very slight compromise in correlation (0.78 to 0.77) when compared to the initial model and still explained for 59.2% of the variation in warfarin dose. Data from remaining subjects (n = 109) were used to validate this derived model. It showed an overall under-prediction of 0.37 \pm 1.26 mg/day, ranging from -5.1 to 2.4 mg/day.

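### The primary t-test is valid but makes no use of age, weight or site; prespecified adjustment could narrow the interval set against the 0.5 margin, by an unknown and possibly negligible amount

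*SAP*

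**What the plan says.** SAP 7.1 defines the outcome and the test: "The primary endpoint is the number of dose titrations performed up to 12-14 days following the initiation of warfarin therapy", and "The average number of dose titration will be compared between study groups using the Student's t-test". No covariate, site term or adjusted sensitivity analysis for this endpoint appears in the SAP or in the protocol text bound with it.

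SAP section 4 has patients "randomised 1:1 to receive pharmacogenetics-guided or the traditional dosing regimen". The SAP's executive summary lists three sites, two in Singapore and one in Malaysia.

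Protocol 4.3 says which baseline characteristics are collected: "These include race, age, sex, weight, height, liver and renal function, and concomitant medications".

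Protocol 4.4 describes how the dose model was built. The initial model "featured the patient age, body weight, Indian and Chinese ethnic groups as well as the pharmacogenetic predictors". The two ethnic terms and CYP2C9*2 were then removed. Age and weight are not among the terms reported as removed. The final model explained 59.2% of the variation in warfarin dose.

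SAP section 5 gives the design figures: "The sample size of 270 (135 in each study arm) provides 80% power to detect a non-inferiority margin of 0.5". The other inputs stated there are a 5% one-sided level, mean titration counts that differ by 1.0 between the arms, and an SD of 1.4 in both.

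**The concern.** A two-sample t-test leaves all between-patient variation in the error term. If some of it can be explained by characteristics fixed before treatment, a prespecified regression on those characteristics estimates the same mean difference with a smaller standard error. It also corrects the estimate for chance imbalance in them.

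Here the candidates are already to hand. Age and weight bear on how much warfarin a patient needs. In the traditional arm the first doses in protocol 4.2 are nearly fixed, with an age rule on one day and no weight term, so patients whose needs differ from that schedule may be the ones whose dose is changed. Site could matter because protocol 4.2 and the appendices leave some latitude in the number of early visits and the timing of INR rechecks.

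What is at stake is the width of the interval compared with the 0.5 margin. The type I error rate is not in question.

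**Working it through.** **Inputs.** From SAP section 5: margin 0.5, SD 1.4, one-sided alpha 0.05 (z = 1.645), 135 per arm. The R-squared of site, age and weight for the titration count is not in the documents, so it is assumed.

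**The plan's own figure first.** With a true difference of 0, n per arm = 2 × (z for alpha + z for power)² × SD² / margin².
- 80% power: 2 × (1.645 + 0.842)² × 1.96 / 0.25 = 96.9, so 97 per arm and 194 in total.
- 90% power: 2 × (1.645 + 1.282)² × 1.96 / 0.25 = 134.3, so 135 per arm and 270 in total.

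The planned 270 therefore matches 90% power, not the stated 80%. The stated difference of 1.0 has no visible part in this. If it favours pharmacogenetics, the distance to the margin is 1.0 + 0.5 = 1.5, 11 per arm would give 80%, and power at 135 per arm is essentially 100%. The baseline below is the one that returns 270: a true difference of 0.

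**Unadjusted analysis.** SE = 1.4 × √(2/135) = 0.170. The half-width of the two-sided 90% interval is 1.645 × 0.1704 = 0.280. Power = Φ(0.5/0.1704 − 1.645) = Φ(1.289) = 90.1%.

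**Adjusted analysis.** Replace SD by 1.4 × √(1 − R²). The equivalent unadjusted total is 270/(1 − R²).

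| Assumed R² | SE | 90% CI half-width | Power | Equivalent total N |
|---|---|---|---|---|
| 0 | 0.170 | 0.280 | 90.1% | 270 |
| 0.02 | 0.169 | 0.277 | 90.6% | 276 |
| 0.05 | 0.166 | 0.273 | 91.4% | 284 |
| 0.10 | 0.162 | 0.266 | 92.6% | 300 |
| 0.20 | 0.152 | 0.251 | 94.9% | 338 |

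**Cost of the extra terms.** Site (two terms), age and weight add k = 4 parameters, so residual degrees of freedom fall from 268 to 264. With covariates of no value, randomisation inflates the variance on average by about (N − 3)/(N − k − 3) = 267/263 = 1.015. The half-width would then be 0.280 × √1.015 = 0.282. The table leaves this out. Adjustment breaks even at an R² of about 1 − 263/267 = 0.015, so the 0.02 row is close to no net gain.

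**The case against.** The strongest case against is that nothing here is an error. Under 1:1 randomisation, with no stratification described, the unadjusted t-test is valid. Its interval already allows for chance imbalance, and it matches a sample size built on an unadjusted SD of 1.4. All of that stands.

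The evidence for the covariates is also indirect:
- Protocol 4.4 models maintenance dose, not the number of changes in the first two weeks.
- In the pharmacogenetics arm the dose comes from a model in which age and weight appear to have been kept, so their effect may be largely absorbed there. The traditional schedule already has an age rule.
- Appendices 1B and 2B change the dose both when INR is low and when it is high. Titration count need not rise or fall steadily with dose need, and linear terms may capture little.
- Protocol 4.1 puts all INR-based adjustments under one clinic's protocol, which may limit differences between sites.

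These points stand too. They limit the likely gain but do not show that adjustment would do harm.

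Two stronger readings are tempting. A reader might infer that site, like age and weight, predicts dose need. No section says so, and site was not a candidate predictor in protocol 4.4. A reader might also take the 59.2% as the variance that adjustment would remove. That figure concerns dose and includes genotype, which the proposed model does not.

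**Conclusion.** This is a modest possible gain in efficiency that the plan does not take up. It is a desirable improvement, not a correction. Under the stated SD, 135 per arm and a true difference of 0, an assumed R-squared of 0.02 to 0.10 adds about 0.5 to 2.5 percentage points of power to 90.1% and takes 0.003 to 0.014 off a half-width of 0.280, before the small cost of the extra terms. Higher values of R-squared have no anchor in the documents. If the true difference favours pharmacogenetics by the stated 1.0, power is already close to 100% and adjustment adds nothing to it, though the interval could still narrow.

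A reader might infer that the t-test biases the comparison or invalidates the non-inferiority conclusion. The documents do not support that.

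**What to change.** In SAP 7.1, before any comparison of the arms:
- Make the primary estimate the adjusted difference in mean titrations, pharmacogenetics minus traditional, from a linear model with arm, site, age and weight.
- Use robust standard errors, because the outcome is a count and its variance may differ between arms.
- State a simple rule for missing baseline values, for example filling a missing weight with the mean over both arms combined. Protocol 4.3 says the data will be obtained but does not guarantee that they are complete.
- State that the upper one-sided 95% confidence limit is compared with 0.5. SAP 7.1 does not at present link its test to the margin.
- Keep the unadjusted difference as a sensitivity analysis.

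The scale and the margin are unchanged and no new data are needed. The cost is a few sentences in the SAP and four degrees of freedom. The covariates have to be fixed in advance: in an open-label trial, adding them after results are seen would not be credible.
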